	Antibiotic prescriptions	
 
Penicillin/beta-lactams, macrolides, cephalosporins, doxycycline, others, defined using country-specific codes (ATC, AIC, Other) (Appendix 4)
 
	
 
Binary variable (yes/no for each class of medication prescribed)
 
Continuous variable (number of prescriptions, length of treatment in days)
 
Measurement in the 12-month baseline period
 

	Comorbidities	
 
Smoking status and alcohol use, as recorded in the database
 
	
 
Binary variable (yes/no)
 

Objective	Outcome	Definition	Measurement
		
 
COPD (including CB), chronic lung disease, asthma, immunocompromised conditions, kidney diseases, liver diseases, cancer, malnutrition, food allergy, congenital malformations of the respiratory tract, ischaemic stroke, heart failure, atrial fibrillation, myocardial infarction, coronary heart disease, diabetes, gastro-oesophageal reflux, allergic rhinitis, atopic dermatitis, defined as <math>\geq 1</math> record of the ICD-9/ICD-10 codes (Appendix 3)
 
	
 
Measurement in the 12-month or the maximum baseline period. The maximum baseline period will be used for selected comorbidities that could have occurred earlier but may not be recorded in the data during the 12-month baseline period, such as allergies (allergic rhinitis and food allergy), myocardial infarction and cancer. These will be detailed in the SAP
 

	Overall and RTI-specific healthcare resource utilisation 	
 
Overall and RTI-specific visits, where RTI-specific visit is defined as a healthcare visit associated with an RTI diagnosis code
 
Type of healthcare visit: primary care / outpatient care visit, emergency care visit, hospital admission, ICU admission
 
Number of visits
 
Length of stay (for hospitalisation and ICU stays)
 
	
 
Continuous variable (number of visits, length of stay in days)
 
Measurement in the 12-month baseline period
 

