Pneumonia due to other infectious organisms, not elsewhere classified	J16	Pneumonia due to other infectious organisms, not elsewhere classified
Pneumonia in diseases classified elsewhere	J17	Pneumonia in diseases classified elsewhere
Pneumonia, organism unspecified	J18	Pneumonia, organism unspecified
Acute bronchitis	J20	Acute bronchitis
Acute bronchiolitis	J21	Acute bronchiolitis
Unspecified acute lower respiratory infection	J22	Unspecified acute lower respiratory infection
Peritonsillar abscess	J36	Peritonsillar abscess
Bronchitis, not specified as acute or chronic	J40	Bronchitis, not specified as acute or chronic
Simple and mucopurulent chronic bronchitis	J41	Simple and mucopurulent chronic bronchitis
Unspecified chronic bronchitis	J42	Unspecified chronic bronchitis
Abscess of lung and mediastinum	J85	Abscess of lung and mediastinum
Pyothorax with fistula	J86	Pyothorax with fistula
Chronic Obstructive Pulmonary Disease (COPD), including chronic bronchitis (CB)		
Bronchitis	J40	Bronchitis, not specified as acute or chronic
Simple and mucopurulent chronic bronchitis	J41	Simple and mucopurulent chronic bronchitis
Unspecified chronic bronchitis	J42	Unspecified chronic bronchitis
Emphysema	J43	Emphysema
Other chronic obstructive pulmonary disease; including chronic bronchitis (CB)	J44	Other chronic obstructive pulmonary disease

Variables: Label For Diseases Used In The Study	ICD-10 Code	ICD-10 Code Label Used in the Study
Chronic obstructive pulmonary disease exacerbations	See algorithm below	See algorithm below
Chronic lung disease		
Chronic respiratory disease originating in the perinatal period	P27	Chronic respiratory disease originating in the perinatal period
Wilson-Mikity syndrome	P27.0	Wilson-Mikity syndrome
Cystic fibrosis	E84	Cystic fibrosis
Cystic fibrosis with pulmonary manifestations	E84.0	Cystic fibrosis with pulmonary manifestations
Other pulmonary heart diseases	I27	Other pulmonary heart diseases
Coal-worker pneumoconiosis	J60	Coal-worker pneumoconiosis
Pneumoconiosis due to asbestos and other mineral fibres	J61	Pneumoconiosis due to asbestos and other mineral fibres
Pneumoconiosis due to dust containing silica	J62	Pneumoconiosis due to dust containing silica
Pneumoconiosis due to other inorganic dusts	J63	Pneumoconiosis due to other inorganic dusts
Hypersensitivity pneumonitis due to organic dust	J67	Hypersensitivity pneumonitis due to organic dust
Asthma		
Asthma	J45	Asthma

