Severe asthma	J46	Status asthmaticus
Asthma exacerbation		
Mild intermittent asthma with (acute) exacerbation	J45.21	Mild intermittent asthma with (acute) exacerbation
Mild persistent asthma with (acute) exacerbation	J45.31	Mild persistent asthma with (acute) exacerbation
Moderate persistent asthma with (acute) exacerbation	J45.41	Moderate persistent asthma with (acute) exacerbation
Severe persistent asthma with (acute) exacerbation	J45.51	Severe persistent asthma with (acute) exacerbation
Unspecified asthma with (acute) exacerbation	J45.91	Unspecified asthma with (acute) exacerbation
Immunocompromised conditions, please see diagnoses used in the definition in Section 8.7		
Kidney diseases		
Essential hypertension	I10	Essential (primary) hypertension

Variables: Label For Diseases Used In The Study	ICD-10 Code	ICD-10 Code Label Used in the Study
Hypertensive heart disease	I11	Hypertensive heart disease
Hypertensive renal disease	I12	Hypertensive renal disease
Hypertensive heart and renal disease	I13	Hypertensive heart and renal disease
Secondary hypertension	I15	Secondary hypertension
Unspecified contracted kidney	N26	Unspecified contracted kidney
Liver diseases		
Alcoholic liver disease	K70	Alcoholic liver disease
Toxic liver disease	K71	Toxic liver disease
Hepatic failure, not elsewhere classified	K72	Hepatic failure, not elsewhere classified
Chronic hepatitis, not elsewhere classified	K73	Chronic hepatitis, not elsewhere classified
Fibrosis and cirrhosis of liver	K74	Fibrosis and cirrhosis of liver
Other inflammatory liver diseases	K75	Other inflammatory liver diseases
Other diseases of liver	K76	Other diseases of liver
Liver disorders in diseases classified elsewhere	K77	Liver disorders in diseases classified elsewhere
Cancer		
Malignant neoplasms	C00 – C97	Malignant neoplasms
In situ neoplasms	D00 – D09	In situ neoplasms
Benign neoplasms	D10 – D36	Benign neoplasms
Neoplasms of uncertain or unknown behaviour	D37 – D48	Neoplasms of uncertain or unknown behaviour
Malnutrition		
Malnutrition	E40 – E46	Malnutrition
Food allergy		
Anaphylactic shock due to adverse food reaction	T78.0	Anaphylactic shock due to adverse food reaction
Other adverse food reactions, not elsewhere classified	T78.1	Other adverse food reactions, not elsewhere classified
Congenital malformations of the respiratory tract		
Congenital malformation of nose	Q30	Congenital malformation of nose

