Variables: Label For Diseases Used In The Study	ICD-10 Code	ICD-10 Code Label Used in the Study
Congenital malformation of larynx	Q31	Congenital malformation of larynx
Congenital malformation of trachea and bronchus	Q32	Congenital malformation of trachea and bronchus
Congenital malformation of lung	Q33	Congenital malformation of lung
Congenital malformation of respiratory system	Q34	Congenital malformation of respiratory system
Ischaemic stroke		
Ischaemic stroke	I63	Cerebral infarction
Heart failure		
Heart failure	I50	Heart failure
Atrial fibrillation		
Atrial fibrillation	I48	Atrial fibrillation and flutter
Myocardial infarction		
Myocardial infarction	I21	Acute myocardial infarction
	I22	Subsequent myocardial infarction
	I25	Chronic ischaemic heart disease
Coronary heart disease		
Coronary heart disease	I25	Chronic ischaemic heart disease
Diabetes		
Diabetes	E10 - E14	Diabetes mellitus
Gastro-oesophageal reflux disease		
Gastro-oesophageal reflux disease	K21	Gastro-oesophageal reflux disease
Allergic rhinitis		
Allergic rhinitis	J30	Vasomotor and allergic rhinitis
Atopic dermatitis		
Atopic dermatitis	L20	Atopic dermatitis
Variables used exclusively for subgroups		
Pregnancy (patients who were pregnant)		
Ongoing pregnancy (not yet delivered)	Z32.1	Pregnancy confirmed
	Z33	Pregnant state
	Z34	Supervision of normal pregnancy

Variables: Label For Diseases Used In The Study	ICD-10 Code	ICD-10 Code Label Used in the Study
	Z35	Supervision of high-risk pregnancy
	Z36	Antenatal screening
Delivery	Z37	Outcome of delivery
	Z38	Liveborn infants according to place of birth
Abortion	O03	Spontaneous abortion
	O04	Medical abortion
	O05	Other abortion
	O06	Unspecified abortion

Note: ICD: International Statistical Classification of Diseases and Related Health Problems; SAP: statistical analysis plan; RTI: Respiratory Tract Infection: URTI: Upper RTI; LRTI: Lower RTI; COPD: Chronic Obstructive Pulmonary Disease; CB: Chronic Bronchitis

ICD-9 codes will be provided in the SAP.

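### Three comorbidity code lists in Appendix 3 (kidney disease, cancer, myocardial infarction) do not match their labels, so the baseline table would report wrong prevalences; the COPD list has a lesser fault of the same kind.

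*Protocol*

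**What the plan says.** Table 8 (Section 3.3.2.2) lists the comorbidities for secondary objective 1, among them "kidney diseases, liver diseases, cancer, malnutrition", as well as COPD including chronic bronchitis, myocardial infarction and coronary heart disease. Each is a yes/no variable, positive on at least one record of the Appendix 3 codes.

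Appendix 3, Table 10 gives these lists:

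- **Kidney diseases:** I10 ("Essential (primary) hypertension"), I11 (hypertensive heart disease), I12 ("Hypertensive renal disease"), I13 (hypertensive heart and renal disease), I15 ("Secondary hypertension") and N26 ("Unspecified contracted kidney").
- **Cancer:** C00-C97 (malignant), D00-D09 (in situ), D10-D36 ("Benign neoplasms") and D37-D48 (uncertain or unknown behaviour).
- **Myocardial infarction:** I21, I22 and I25 ("Chronic ischaemic heart disease").
- **Coronary heart disease:** I25 only.
- **COPD, including chronic bronchitis:** J40 ("Bronchitis, not specified as acute or chronic"), J41, J42, J43 and J44.

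Section 3.3.3 makes selected comorbidities candidates for the PS, stresses smoking and respiratory conditions (naming COPD), and leaves the final set to the SAP. Section 3.9.1.2 says the success of the matching will be shown through the descriptive baseline results. The ICD-9 codes are also left to the SAP; the ICD-10 codes are fixed in the protocol.

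**The concern.** A variable reported as kidney disease, cancer or MI should measure that condition. As the lists stand, a patient with uncomplicated hypertension has kidney disease, a patient with a benign tumour has cancer, and a patient with chronic ischaemic heart disease has had an MI. A patient whose only kidney record is a kidney-failure code is not flagged at all.

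Two uses of these variables are at stake. The first is direct: the baseline table would describe the two exposure groups under labels that do not fit, and the same table is offered as evidence that matching worked. The second is conditional: if the SAP takes any of these variables into the PS, matching would balance something other than the condition named.

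The COPD list raises a smaller question of the same kind. One bronchitis record that the coder did not classify as acute or chronic is enough to mark a chronic disease, in a cohort selected for respiratory infection and open from age 1 year (Table 4).

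**Working it through.** The protocol gives no figure to reproduce here. The check compares each list with its label and traces where the variable is used.

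**Kidney diseases.** The six codes are I10, I11, I12, I13, I15 and N26.
- Hypertension categories: I10, I11, I12, I13, I15 = 5 of 6.
- Labels that do not name the kidney: I10, I11, I15 = 3 of 6.
- Kidney code outside hypertension: N26 = 1 of 6.
- Codes labelled as kidney failure or chronic kidney disease: 0.

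**Cancer.** Three-character categories, counted by range arithmetic:
- C00-C97 = 98, D00-D09 = 10, D10-D36 = 27, D37-D48 = 12; total 98 + 10 + 27 + 12 = 147.
- Benign: 27/147 = 18%. Uncertain or unknown behaviour: 12/147 = 8%. Neither malignant nor in situ: 39/147 = 27%.
- These are shares of code categories, not of patients.

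**Myocardial infarction and coronary heart disease.** MI = {I21, I22, I25}; coronary heart disease = {I25}. The second set lies inside the first. Coronary heart disease = yes therefore forces MI = yes, and the cell with coronary heart disease but no MI is empty by construction. This follows from the two lists alone. If both variables were entered in the PS, they would be nested.

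**COPD.** J40 is in the list and, by its own label, is not specified as chronic. Table 8 needs only one record. Section 3.9.2.2 uses the maximum baseline period for chronic conditions, so an old record suffices. The feasibility counts in Section 3.5 show how many children are involved: in China 8,656 - 1,338 = 7,318 of 8,656 OM-85 users (85%) were under 18. These are feasibility counts; the protocol expects fewer OM-85 patients in the study itself.

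**Where the variables go.** Table 8 takes all of them into the secondary objective 1 baseline table. Section 3.9.1.2 uses the descriptive baseline results to judge the matching. Section 3.3.3 makes comorbidities PS candidates only.

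**Illustration on assumed values (the protocol gives no prevalences).** Let h be the share of patients with I10, I11 or I15, and k the share with I12, I13 or N26, taken as independent. The share of patients flagged with kidney disease who carry any code naming the kidney is k / (1 - (1 - h)(1 - k)).
- h = 5%, k = 5%: 0.05 / (1 - 0.95 × 0.95) = 0.05 / 0.0975 = 51%.
- h = 20%, k = 2%: 0.02 / (1 - 0.80 × 0.98) = 0.02 / 0.216 = 9%.
- h = 40%, k = 1%: 0.01 / (1 - 0.60 × 0.99) = 0.01 / 0.406 = 2.5%.

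The range over h = 5-40% and k = 1-5% is 2.5% to 51%. It shows direction only, and it leaves out patients with kidney failure whom the list misses.

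**The case against.** The mismatch between codes and labels cannot be argued away: these rows are readable, and nothing else in the protocol narrows them. The case on the other side is about consequences, and much of it stands.

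- **The PS.** A reader might infer that the PS is misspecified. The protocol does not support that. Section 3.3.3 only considers these variables, puts the weight on smoking and respiratory conditions, and leaves the choice to the SAP, which is not at hand. Nothing in the protocol commits kidney disease, cancer, MI or coronary heart disease to the PS.
- **COPD and RTI history.** A reader might infer that J40 makes the COPD variable repeat the RTI history. The upper, lower and other RTI code lists are blacked out, so the overlap cannot be confirmed. J40 also appears among infection-related complications, but that is a separate heading, and RTI history in the PS is described by upper/lower/other type and number.
- **Codes under two headings.** J40, J41 and J42 appear both as infection-related complications and as COPD. That is not an error in itself, since the two lists may serve different purposes. J41 and J42 fit a COPD heading that expressly includes chronic bronchitis. Only J40 is open to question.
- **How many patients.** A reader might conclude that most patients flagged with kidney disease have only hypertension. The protocol gives no prevalences, and the answer differs by age. Section 3.4.2 says most OM-85 patients in China are under 11, where hypertension codes would matter little.
- **Reach.** The readable subgroups in Table 5 do not use kidney disease, cancer or MI, and no effect on either primary objective is shown.

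It does not stand as an answer that the SAP will settle the matter. The SAP is to supply the ICD-9 codes and the PS set; Table 8 already ties these variables to the ICD-10 lists in Appendix 3.

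**Conclusion.** The kidney disease, cancer and MI lists are wrong as written. Three of six kidney codes do not name the kidney and no kidney-failure or chronic-kidney-disease code is present; the cancer list covers benign and uncertain-behaviour neoplasms; and coronary heart disease lies wholly inside MI. Following the plan would give wrong prevalences in the secondary objective 1 baseline table and in the evidence offered for PS balance.

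The overlap of coronary heart disease with MI is complete under the protocol's own lists. It does not mean that every possible coronary code falls under MI. The size of the other errors in patients, and any bias in the incidence rate ratio, cannot be computed from the protocol. For kidney disease, cancer and MI the bias is probably small next to RTI history and respiratory comorbidity, and it arises only if the SAP puts these variables in the PS.

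J40 in the COPD list is a fair secondary point, because COPD is a named PS candidate and one unspecified bronchitis record sets it. The point should be corrected before data extraction; it does not overturn either primary objective.

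**What to change.** Edit Appendix 3, Table 10 before extraction:

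- **Kidney diseases:** move I10, I11 and I15 to a separate hypertension covariate. Define kidney disease by I12, I13, N26 and the ICD-10 renal-failure and chronic-kidney-disease categories (N17-N19).
- **Cancer:** restrict to C00-C97. Report in situ (D00-D09) and uncertain-behaviour (D37-D48) neoplasms separately and drop D10-D36.
- **Myocardial infarction:** remove I25 and keep it under coronary heart disease.
- **COPD:** remove J40, or count it only together with a further COPD code. J41 and J42 can stay where they are.
- **ICD-9:** make the same edits in the lists to be given in the SAP. This matters for Italy, which uses both revisions (Section 3.3).

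The work is a code-list edit with no change to design or study size. It is not entirely free: version 2.0 handled Appendix 3 code changes as an amendment, and Section 4.3 requires approval of amendments by the ethics committee of the Tianjin main centre.

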**Figure 1 Study Design**

Note: CED: cohort entry date; RTI: respiratory tract infection; SOC: standard of care

-  For the patients who initiate OM-85 during the initiation grace period, another index date is assigned at the date of the 1st OM-85 prescription: OM-85 initiation date. This date is used as the index date in analyses on exclusively OM-85 initiators.
-  Outcomes defined for each objective are listed in [Table 7](#) and [Table 8](#).
-  Pregnancy at CED is estimated using a variable assessment window expanding from 183 days (6 months) before CED to 280 days (9 months) after CED, as detailed in [Section 3.2.2.3](#).
-  Selected covariates are defined during initiation grace period, to be used in sensitivity analysis for clone censor weighting.

period (see [Section 3.3.3](#)).

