	
been pregnant at CED if they fulfil any of the following definitions:
 
≥ 1 record of ICD-9/ICD-10 codes for ongoing pregnancy within 6 months before CED AND no record of delivery or abortion within 6 months before CED
 
OR
 
≥ 1 record of ICD-9/ICD-10 code for ongoing pregnancy at CED or during follow-up, at longest 6 months after CED
 
OR
 
≥ 1 record of ICD-9/ICD-10 code for abortion at CED or during follow-up, at longest 3 months after CED
 
OR
 
≥ 1 record of ICD-9/ICD-10 code for delivery at CED or during follow-up, at longest 9 months after CED
	
Patients aged ≥ 65 years at CED	Based on age at CED	
Patients aged ≥ 80 years at CED	Based on age at CED	
Patients with immunocompromised conditions at CED	≥ 1 record of ICD-9/ICD-10 codes or ATC codes defined in Appendix 6, during the maximum baseline period or shorter as detailed in Appendix 6	
Subgroups of OM-85 initiators based on OM-85 treatment cycle length and number		

OM-85 initiators, who had
 
 
• 1 treatment cycle of < 90 days
 
• 1 treatment cycle of 90 days 
 
• 1 treatment cycle of > 90 days to ≤ 180 days
 
• 1 treatment cycle of > 180 days
 
• 2 treatment cycles
 
	Defined based on the variables described in Section 3.3.1.2	
 
• Primary objective 1, secondary objective 3
 

Note: ATC: Anatomical Therapeutic Chemical; **CCI**; CED: cohort entry date; **CCI**; **CCI**; COVID-19: coronavirus disease 2019; ICD-9: ICD-10: International Statistical Classification of Diseases and Related Health Problems 9th Revision; International Statistical Classification of Diseases and Related Health Problems 10th Revision; RTI: respiratory tract infection.

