Exploratory objective [redacted]	CCI [redacted] CCI [redacted]	CCI [redacted] CCI [redacted] CCI [redacted] CCI [redacted] CCI [redacted] CCI [redacted] CCI [redacted]	CCI [redacted] CCI [redacted] CCI [redacted] CCI [redacted] CCI [redacted]
Exploratory [redacted]	CCI [redacted] CCI [redacted]	CCI [redacted] CCI [redacted] CCI [redacted] CCI [redacted] CCI [redacted] CCI [redacted]	CCI [redacted] CCI [redacted] CCI [redacted] CCI [redacted]
Exploratory objective [redacted]	CCI [redacted] CCI [redacted] CCI [redacted]	CCI [redacted] CCI [redacted] CCI [redacted] CCI [redacted] CCI [redacted]	CCI [redacted] CCI [redacted] CCI [redacted] CCI [redacted] CCI [redacted]
Exploratory objective [redacted]	CCI [redacted] CCI [redacted] CCI [redacted]	CCI [redacted] CCI [redacted] CCI [redacted] CCI [redacted] CCI [redacted]	CCI [redacted] CCI [redacted] CCI [redacted] CCI [redacted] CCI [redacted]

Objective	Outcome	Definition	Measurement
Exploratory objective CCI	CCI CCI CCI	CCI CCI CCI CCI	CCI CCI CCI CCI CCI CCI CCI
Exploratory objective CCI	CCI CCI CCI	CCI CCI CCI CCI	CCI CCI CCI CCI CCI CCI CCI

CCI

 THIN databases (Italy and Belgium) do not cover hospitalisation stays or visits to the ICU or emergency care, while the Inspur database (China) does not cover primary care.

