#### **3.9.2.2 Outcome Misclassification/Information Bias**

As this is a retrospective study using healthcare databases, diagnosis codes are used to capture RTIs. Based on the feasibility study, diagnosis codes for RTIs are captured in the data sources. Nonetheless, there is a possibility that not all RTI cases are recorded in the data sources, especially since the data sources do not represent all healthcare settings: THIN in Belgium and Italy represents exclusively primary care, and Inspur in China secondary/tertiary care. Overseeing some RTIs would result in underestimating the rate of RTI episodes, which in turn would likely bias towards the null, i.e., the possible protective effect of OM-85 is more difficult to detect, which shall be considered in the interpretations.

In addition, RTI episodes (primary outcome) are not directly available in the data sources, nor are the variables used in trials (43–46) to define RTI episodes. Therefore, RTI episodes are defined based on observed time between records of RTI diagnoses, 14 days (main RTI definition). While this maximum length of an RTI episode was developed in collaboration with clinicians, the duration could lead to underestimating or overestimating the true number of RTIs, which may differ depending on if a patient had mostly URIs or LRIs, as well as for children and other ages. The descriptive results on the type of infections recorded in baseline will provide further information on the validity of the time frame of an RTI episode for the study population.

Additionally, alternative definitions for RTIs using baseline data will be explored in Step 1 of the analysis, as detailed in Section 3.7.8: a simple and complication RTI definition (Section 3.3.2.1). A sensitivity analyses will also be performed for different lengths of RTI episodes, 7 and 21 days. These will inform about the robustness of the main RTI definition, to be considered in the interpretation of the results.

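### In ICD-10, Table 10 leaves Z37 as the only code for the mother's delivery, so the first pregnancy clause in Table 5 can keep women who have already delivered, most plausibly in THIN

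*Protocol*

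**What the plan says.** Table 5 (Section 3.2.2.3) defines women estimated to be pregnant at CED by four alternatives; meeting any one is enough. In short:

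1. a pregnancy code in the 6 months before CED, "AND no record of delivery or abortion within 6 months before CED";
2. a pregnancy code at CED or up to 6 months after;
3. an abortion code at CED or up to 3 months after;
4. a delivery code at CED or up to 9 months after.

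Note 3 to Figure 1 gives the same window, "expanding from 183 days (6 months) before CED to 280 days (9 months) after CED".

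Table 10 (Appendix 3) supplies the ICD-10 codes. Ongoing pregnancy is Z32.1 and Z33 to Z36. Delivery is Z37, labelled "Outcome of delivery", and Z38, labelled "Liveborn infants according to place of birth". Abortion is O03 ("Spontaneous abortion"), O04, O05 and O06. The ICD-9 codes, which Italy also uses (Section 3.3), are left to the SAP.

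On coverage, footnote 2 to Table 8 states that "THIN databases (Italy and Belgium) do not cover hospitalisation stays or visits to the ICU or emergency care", and Section 3.9.2.2 adds that "THIN in Belgium and Italy represents exclusively primary care, and Inspur in China secondary/tertiary care". Section 3.9.2.3 expects misclassification of pregnancy and says the subgroup may be too large or too small. It names no cause.

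**The concern.** The first clause infers a continuing pregnancy from the absence of an end record. It sets no gestational limit and asks for nothing after CED. For pregnancies that end in birth, its accuracy therefore rests on how completely the mother's delivery is recorded under the listed codes.

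That recording looks weak for two reasons. The code list has one code that describes the mother's delivery and one that describes her child. And the two THIN databases hold GP records without hospital stays.

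Pregnancy is listed among the vulnerable populations, with all objectives applicable. If the subgroup is analysed, results carrying that label could partly describe women after delivery. Nothing in the protocol's described output would show how many.

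**Working it through.** The protocol states no figure on this point, so there is none to reproduce. The check has two parts.

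**Rule against code list.** For a woman whose pregnancy ended before CED and who has a pregnancy code in the look-back:

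- If it ended in abortion, any of four maternal codes removes her from the first clause.
- If it ended in birth, Z37 removes her. Z38 does so only if the infant's code was entered in her own record. Section 3.4.1 describes THIN as non-linkable, and no mother-infant link is described anywhere.
- If neither kind of record is found, she is classed as pregnant.

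The fourth clause uses the same delivery codes in the other direction. A woman who was pregnant at CED, and whose only evidence is a later delivery, is lost if that delivery is not recorded.

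**Possible size for the first clause.** Two inputs are missing from the protocol: the share *s* of deliveries visible in the database, and when in pregnancy the codes are entered. Both are assumed below.

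*Model A (one pregnancy code).* The code falls uniformly between gestation months 2 and *b*, CED falls uniformly over the next 6 months, and birth is at month 9. The share already delivered at CED is

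p = [1/(b − 2)] × ∫ from 3 to b of (g − 3)/6 dg = (b − 3)² / [12(b − 2)].

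- b = 9: 36/84 = 43%
- b = 5: 4/36 = 11%
- b = 4: 1/24 = 4%

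Among women the clause retains, the post-partum share is p(1 − s) / [(1 − p) + p(1 − s)]:

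| Code timing | s = 0 | s = 0.5 | s = 0.8 |
|---|---|---|---|
| months 2–9 | 43% | 3/11 = 27% | 3/23 = 13% |
| months 2–5 | 11% | 1/17 = 6% | 1/41 = 2% |
| months 2–4 | 4% | 1/47 = 2% | 1/116 = 1% |

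*Model B (codes throughout pregnancy).* Delivery is at day 280, CED is uniform in time, the first code is at day 42 or 84, and the last code lies between day 220 and day 280. The look-back is 183 days (Figure 1, note 3). Let G be the days from first code to delivery (280 − 42 = 238, or 280 − 84 = 196). Let P be the days after delivery with a code still in the look-back (220 + 183 − 280 = 123, up to 280 + 183 − 280 = 183). The post-partum share is P(1 − s) / [G + P(1 − s)].

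- s = 0: from 123/361 = 34% to 183/379 = 48%
- s = 0.5: from 61.5/299.5 = 21% to 91.5/287.5 = 32%
- s = 0.9: from 12.3/250.3 = 5% to 18.3/214.3 = 9%
- s = 1: 0%

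Across both models with no deliveries visible, the range is about 4% to 48%.

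**The case against.** The strongest reply is that the protocol already discloses the risk. Table 5 says estimated, and Section 3.9.2.3 expects misclassification in either direction. The subgroup is also optional: Section 3.2.2.3 makes it conditional on a decision to run it and on patient counts. All of that is true, and it limits the importance of the point. It does not change a rule that, followed as written, reads a missing record as a continuing pregnancy.

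Several stronger readings are tempting, and the documents do not support them:

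- *That THIN cannot see deliveries at all.* The protocol says hospital stays are absent. It does not say that a GP never enters Z37 after a hospital birth, and it gives no capture rate. Abortion codes also operate. Under-recording is likely; its extent is unknown.
- *That the failure is the same in all three countries.* Inspur holds records from 82 hospitals (Section 3.4.2), so the missing-hospital argument does not reach China. Only the narrow code list does.
- *That some 43% of the pregnancy subgroup would be post-partum.* That figure needs codes spread evenly to month 9 and no visible deliveries. Z32.1, pregnancy confirmed, is plausibly an early code, and early codes bring the share down to 11% or 4%. Every figure concerns one of four alternative clauses, not the subgroup.
- *That the error runs one way.* Missing deliveries also cost the fourth clause women who were pregnant, so the net direction is open.

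It is also fair that Z38 is probably inert. Patients must be at least 1 year old with 12 months' prior enrolment, so a newborn's own code should not matter, and deleting it reclassifies nobody if it never appears in mothers' records. Its relevance is that the delivery list has less in it than its two entries suggest.

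**Conclusion.** The point holds as a limited defect in a code list and one classification clause. In ICD-10, delivery rests in effect on Z37 alone, while the first clause of Table 5 treats silence as pregnancy. Where deliveries are under-recorded, women who have delivered can stay in the subgroup and some pregnant women can be missed by the delivery clause.

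The size cannot be established from the protocol. With no deliveries visible, roughly 4% to 48% of the women retained by the first clause would be post-partum, depending on assumed code timing; the share falls as capture rises and is zero with full capture. That deliveries are under-recorded in THIN is an inference from the lack of hospital stays. The statement about delivery codes is confined to ICD-10, because the ICD-9 list is deferred to the SAP. No overall-population estimate is affected, since Table 10 reserves these codes for subgroups. The point is minor but cheap to put right.

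**What to change.** 1. In Table 10, add the maternal obstetric delivery codes alongside Z37 and remove Z38 from the mother's delivery codes. Provide matching ICD-9 codes for Italy. This helps both the pre-CED exclusion and the post-CED delivery clause.
2. Added codes cannot recover a delivery that never reaches the GP record. In THIN, therefore, report how many women enter the subgroup through the first clause alone, and show the subgroup result with and without them.

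Do not replace the first clause with a mandatory confirming record on or after CED. The other three clauses already admit women with such records, so this would largely delete the first clause. Where deliveries are under-recorded, it would also drop women who really were pregnant.

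The cost is a code-list edit with no new data, probably a slightly smaller subgroup, and one extra table.
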